Lacerations and accidental incisions are a common presenting complaint in Emergency Departments (EDs). According to the CDC, there were over 4 million ED visits in 2010 that involved suturing or stapling (1). A wound registry created by faculty at SUNY Stony Brook compiled a cohort of 1000 patients with wounds requiring sutures. Of their cohort, they found that 28% of these wounds were located on either the finger or hand (2). These numbers suggest that there are over 1 million hand and feet lacerations repaired at EDs in America every year. Traditional therapy for lacerations include suture repair with non-absorbable sutures and still remains the "gold standard" for repair and cosmetic outcome. In recent years, there have been numerous studies investigating alternative therapies to standard suture repair. Studies have shown non-inferiority of both absorbable sutures, topical adhesives, and adhesive strips in simple lacerations in both the adult and pediatric population (3,4,5,6). Studies in the biology of wound healing have shown that the three stages of healing, inflammation, epithelialization, and maturation, occur regardless of whether wounds were closed or left open (7,8). A recent study by Quinn, et al, in the general population showed no significant difference in cosmetic appearance and patient satisfaction of suture repair or conservative management (non-repair) in lacerations (9). There have also been investigations that challenge the past standards of care in pre-repair wound management. It has been observed that there was a decreased infection rate in suture-less laceration repairs, when compared to traditional suturing (10). The use of povidone-iodine as irrigation medium has been shown to delay wound healing and reduce wound strength (11). Running water has been shown to have equivalent infection rates as high-pressure irrigation with sterile saline (12). Another study found no increased infection rate when comparing sterile versus non-sterile technique in the repair procedure (13, 14). When you consider the time, cost, and pain involved in traditional suture repair procedures, a method decreasing all three of these factors without any increase in infection rates or decrease in patient satisfaction seems to be beneficial for both patients and the Emergency Departments that serve them. This earlier referred study by Quinn serves as the starting point for the current proposed investigation. This study found non-inferiority of suture versus conservative repair of simple hand lacerations, in both cosmetic outcomes and infection rates.

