Our primary hypothesis is that there is no difference in cosmetic outcomes between suture repair and conservative treatment of simple, superficial (<2cm) hand and feet lacerations in the pediatric population. Secondary measures will be infection rates, pain scores, time to return to normal activity, time of initial ED visit, and cost of supplies used in repair. Our aim is to show that conservative repair saves time, money and reduces patient pain compared to traditional suture repair, while having no decrease in cosmetic satisfaction or infection rates.

Please save frequently

c) Describe the study design (e.g., single/double blind, parallel, crossover, control, experimental, observational, etc.). If the study is investigator-initiated, a timeline for individual subject recruitment, follow-up, and analysis for the study is required. Also, indicate if the subjects will be randomized.

We will use a prospective clinical trial with computer generated randomization to test our hypothesis. Patients will be recruited by a qualified pediatric emergency physician. Once consent is obtained from the parent(s)/legal guardians, patient data will be collected. The patient will have their hand or foot laceration(s) treated in the emergency department at that time by an attending physician, PEM fellow, or senior resident. The patient will then follow-up in 10-14 days for a wound check and satisfaction survey, and then again at 3-4 months for repeat survey and photograph of the healed wound. Our timeline for recruitment is approximately 15-18 months, 12-15m for recruitment, plus 3 months for additional follow-up visits. Analysis of the data should take an additional month.

Protocol Title: Conservative versus Suture Repair of Hand and Feet Lacerations in Children

d) If subjects will be given placebo, please justify placebo use. *?HELP?*

There will be no placebos used in this study.

3. Study Procedures

a) N Is this project a multicenter study (i.e., same project is conducted elsewhere by a different investigator) OR does this study involve conduct of research at multiple sites? Is SLU acting as a coordinating center for other sites OR is the SLU PI a direct recipient of a federal grant for this research? If yes, complete and attach the Supplemental Application for Coordinating Center Activities.
Will the SLU site be participating in all parts/procedures/arms of the study?
If No, explain what SLU will NOT participate in:

Please save frequently

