Patients will be asked to follow-up in the Pediatric Emergency Department in 10-14 days. The patients will have a reminder phone call on day 6-8 for their follow-up visit and arrange for an appointment time. The wounds will be evaluated for complications that were defined a priori as follows: "wound infection" was one that required systemic antibiotics as determined by the treating attending physician; and "wound dehiscence" as a wound that required the placement

Protocol Title:

Conservative versus Suture Repair of Hand and Feet Lacerations in Children

of additional sutures or tissue adhesives. Children in the suture repair group will have their sutures removed. Parents will fill out a follow-up survey at this visit (see Initial Follow-up Survey).

Follow up data will be obtained from the parent or care giver for all subjects in the form of a questionnaire, patient with healing laceration will return with the parent or guardian for inspection of the wound with possible suture removal at 10-14 days then a re-evaluation of the healing wound with digital pictures taken at 3-4 months post ED enrollment for both treatment groups.

Patients will be asked to follow-up in the Pediatric Emergency Department in 12-16 weeks from the initial presentation. The patient will have a reminder phone call in week 11 for this visit and arrangement with time. The parent will fill out a second survey (see Final Follow-up Survey). Photographs of the wound will be taken, using a standardized protocol with a dedicated digital camera, and then printed by a pre-assigned printer. These photographs will be loaded to a computer to prevent alterations.

The photographs will be rated by 3 pediatric emergency physicians on the research team blinded to the treatment assignments. Independent evaluations will enable us to assess inter-observer reliability. The previously validated Visual Analogue Scale (VAS) will be used to assess the cosmetic outcome. The frequently used scale is a 100mm continuous line that is marked on the right end with "best scar" and on the left with "worst scar". The observer will be asked to mark on the line where they believe the scar "best fits". If the patient does not appear for their follow-up visit, a phone call will be made to the parent or guardian, who will be asked to report their satisfaction of the wound on a scale of 1 to 10, with 1 being "very unsatisfied" and 10 being "very satisfied".

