c) If the proposed study is a clinical trial where a drug, vaccine, device or other treatment is compared to a placebo group or comparison treatment group, what are the guidelines or endpoints by which early decisions regarding efficacy or lack of efficacy can be made? For example, it may be reasonable to stop enrollment on a study when efficacy has already been clearly demonstrated, to avoid unnecessary enrollments of additional subjects. Alternatively, it may be reasonable to stop enrollment when it is clear that efficacy will never be demonstrated, given the statistical power of the study as designed. Describe the guidelines that are in place to assist in making these determinations, if relevant to the proposed study.

On an ongoing basis, we will evaluate potential complications and if we identify serious complications related to the study group, we will consider study termination.

d) Describe how data analysis will be performed (statistical tests, methods of evaluating data) and indicate the smallest group/unit for which separate reporting will occur. For studies involving a questionnaire, if data and reliability information are available, please describe or provide references. For full board, unfunded studies describe sample size determination and power analysis. If none, please justify.

Differences between groups will be analyzed using the Student's t-test for independent samples. Proportions will be compared using chi-square and the z-test for independent proportions. A significance level of 0.05 will be used in all analysis. Since this is an equivalence trial, a non-inferiority average difference of 15mm with the cosmesis VAS scale will be considered clinically equivalent. Previous studies have determined that the minimal clinically important differences between two groups ranged from 10 to 15mm (4,15,16).

A sample size of 18 patients per group will be needed to provide a power of 90% with 0.05 alpha error to detect a 15mm difference in the VAS. A patient attrition rate of 40% is expected and with this considered, a total of 50 patients will be enrolled in order to power the study this will include the 20 patients already enrolled in the previous study (#23300).

Protocol Title: Conservative versus Suture Repair of Hand and Feet Lacerations in Children

Please save frequently

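### The plan aims to show that infection is no worse without sutures, but 3(d) offers only a test of difference, with no infection margin or confidence interval

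*Combined protocol and SAP*

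**What the plan says.** The closing sentence of 2(b) describes what the trial intends to show: savings in time, money and pain, "while having no decrease in cosmetic satisfaction or infection rates". Taken literally, a goal of no decrease in infection makes no sense. The background in 1(a) supplies the evident meaning, describing a worthwhile method as one that works "without any increase in infection rates or decrease in patient satisfaction".

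Infection is listed in 2(b) as a secondary measure. Section 3(b) makes it a yes/no outcome, defined by the need for systemic antibiotics, and ties its assessment to the first follow-up visit: "The wounds will be evaluated for complications that were defined a priori as follows".

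The analysis is in 3(d). For binary outcomes it states "Proportions will be compared using chi-square and the z-test for independent proportions", and for every outcome "A significance level of 0.05 will be used in all analysis". It does not say whether tests are one- or two-sided. The only margin concerns cosmesis: "a non-inferiority average difference of 15mm with the cosmesis VAS scale will be considered clinically equivalent". The sample size of 18 per group also rests on cosmesis alone. The visible text gives no infection margin, interval, expected rate or decision rule.

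**The concern.** A test of difference can give evidence that two rates differ. Failing to reject equality does not show that one rate is no higher than the other, least of all in a small trial with a rare event. For cosmesis, 3(d) recognises this and sets a margin. For infection, 2(b) makes the same kind of not-worse claim and 3(d) gives no means of supporting it.

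The documents do not say that a non-significant result will be reported as no increase, but the plan provides no other route to that part of the aim. What is at stake is a reassuring safety statement about leaving children's wounds unsutured, resting on data that could hide a large excess. Without an interval, a reader is not shown how large an excess remains possible.

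No direction is presumed. Section 9.5 lists infection as a risk in both arms, and 1(a) cites an observation that "there was a decreased infection rate in suture-less laceration repairs, when compared to traditional suturing".

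**Working it through.** **The plan's own figure.** There is none for infection. The only stated size is 18 per group, for 15 mm on the cosmesis scale. It cannot be reproduced because no SD is given, and nothing below depends on it beyond using 18 as a denominator.

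**Numbers per arm, assuming an even split.**
- 25: the 50 planned in 3(d), no loss (50/2).
- 18: planned evaluable number in 3(d).
- 15: 50/2 × (1 − 0.40), using the attrition in 3(d).
- 13: 26/2, if the 26 accrued (Continuing Review, item 7) are all there will be, as the response on data safety monitoring in the Comments section indicates.

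The record does not say whether the 26 include the 20 from the earlier study. If they do not, (26 + 20)/2 = 23 per arm, which lies inside this range.

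**Step 1: no infections in either arm.** No assumed rate is needed. The Newcombe 95% limits for 0/n versus 0/n reduce to ± z²/(n + z²), with z² = 3.84. At 18 per arm: 3.84/21.84 = 0.176.

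**Step 2: k infections versus none.** The uncorrected chi-square equals z² with z = √[2kn/(2n − k)]. For k = 2, n = 18: z = √(72/34) = 1.455, two-sided p = 0.146. For k = 3, n = 18: z = √(108/33) = 1.809, two-sided p = 0.070, one-sided p = 0.035.

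| Per arm | 13 | 15 | 18 | 25 |
|---|---|---|---|---|
| 0 v 0: 95% limits (points) | ±23 | ±20 | ±18 | ±13 |
| 2 v 0: observed excess (points) | 15 | 13 | 11 | 8 |
| 2 v 0: 95% interval (points) | −10 to 42 | −9 to 38 | −8 to 33 | −7 to 25 |
| 2 v 0: two-sided p | 0.141 | 0.143 | 0.146 | 0.149 |
| 2 v 0: one-sided p | 0.071 | 0.072 | 0.073 | 0.074 |
| 3 v 0: two-sided p | 0.066 | 0.068 | 0.070 | 0.074 |
| 3 v 0: one-sided p | 0.033 | 0.034 | 0.035 | 0.037 |

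Two versus none is non-significant on either reading. Three versus none is non-significant two-sided and significant one-sided, so the verdict turns on a choice that 3(d) leaves open.

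**Step 3: power of the planned test.** The infection rates are assumptions, because the documents give none. Power is the sum, over all pairs (a, b), of Bin(a; n, p₁) × Bin(b; n, p₂) for tables where the uncorrected test rejects at 0.05. With equal arms, two-sided power is the same whichever arm has the higher rate.

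| Assumed true rates | 13 | 15 | 18 | 25 |
|---|---|---|---|---|
| 5% v 10%, two-sided | 2% | 3% | 4% | 8% |
| 5% v 15%, two-sided | 6% | 9% | 13% | 21% |
| 5% v 20%, two-sided | 14% | 19% | 25% | 38% |
| 5% v 15%, one-sided for the increase | 17% | 21% | 25% | 34% |

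A non-significant result is therefore likely even when the true rate in one arm is three or four times that in the other.

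**The case against.** The strongest reply is that infection is one of several secondary measures in a trial sized for cosmesis. Low power is expected, no interval is planned for any outcome, and counts by arm would let a reader work out the interval. This limits the weight of the point: the primary conclusion is untouched. It does not answer it, because 2(b) makes a not-worse claim for infection and 3(d) supplies no means of judging it.

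A second reply is that the denominators of 15 and 18 are borrowed. The 40% attrition belongs to the cosmesis calculation, and Continuing Review item 10 attributes the withdrawals to missed 4-month visits, whereas infection is assessed at the first follow-up. That is fair, and 25 per arm is the better planning figure if early follow-up is complete. The zero-event limit there is still 13 points.

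A third concerns missing infection status. For a missed visit, 3(b) describes a call to the parent, "who will be asked to report their satisfaction of the wound on a scale of 1 to 10", and mentions no question on infection. The same section also promises questionnaire data from caregivers for every child, and the approved surveys are not in the available text. Some children may therefore have unknown infection status, but that cannot be settled here.

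Finally, the ongoing review of complications in 3(c) and 9.11(b) may be said to cover safety. It sets no threshold and gives no between-arm estimate, so it does not supply the comparison that 2(b) promises.

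**Conclusion.** The concern holds. The aim in 2(b) needs evidence that an excess of infection has been ruled out, and 3(d) provides only a test of difference. Depending on whether 25 or 13 children per arm contribute, the cleanest possible data, with no infections at all, would leave a difference of 13 to 23 percentage points in either direction compatible with the results. That range needs no assumed infection rate. It rests on an even split and a 95% Newcombe interval. The power figures also depend on the assumed rates.

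The fault is the aim as worded together with the missing interval. Using chi-square is not itself an error, and low power for a secondary outcome is not the complaint. The change should be made because the potential to mislead on safety is real and the remedy is cheap.

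**What to change.** **In 2(b)**, replace the infection part of the aim with: *to estimate infection rates in each arm and their difference, with 95% confidence intervals.* State that a non-significant test will not be reported as showing no increase in infection.

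**In 3(d)**, add: *Infection, as defined in 3(b), will be reported by arm as counts over all randomised children with known infection status, including any infection recorded before or outside the first follow-up visit. The number with unknown status will be stated by arm. The risk difference (conservative minus suture) will be given with a 95% confidence interval by a small-sample method such as Newcombe.* The chi-square test may stay as secondary, with its sidedness stated. Dehiscence, also defined in 3(b), can be reported the same way.

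The timing of the first follow-up, which fixes when infection is assessed, differs between 2(a) (7-10 and 14 days) and 2(c) and 3(b) (10-14 days). These must be reconciled.

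**Cost.** Wording only, with no extra patients, and a more modest safety claim. The Continuing Review form requires IRB review before an amendment is used. The Event History shows that approval expired and the third continuing review was withdrawn. If enrolment has ended, the change must be dated and reported as made after enrolment.

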
Please save frequently

b) Describe any animal experimentation and findings leading to the formulation of the study, if

Protocol Title: Conservative versus Suture Repair of Hand and Feet Lacerations in Children

there is no supporting human data.

n/a

2. Purpose of the study

a) Provide a brief lay summary of the project in <200 words. The lay summary should be readily understandable to the general public.

The purpose of this study is to compare outcomes of 2 repair methods in simple (<2cm) hand and feet lacerations in the pediatric population (2-17 yrs). Our hypothesis is that there is no statistical difference in cosmetic outcomes between suture repair and non-repair of these injuries. This study has been performed in the adult population, but has not yet been done in children. We would like to be the first to show that conservative repair can be done in our pediatric population. The suture group will have their injuries repaired with non-absorbable sutures (nylon) which remain the gold standard in cosmetic repair of hands and feet. The conservative group will have identical cleaning and preparation of the wound, but the laceration will be covered with antibiotic ointment and sterile gauze without repair. Secondary outcome measure include patient satisfaction, infection rates, pain during repair, time of initial ED visit stay, and cost of supplies used in repair. Our patients will return in 7-10 and 14 days and in 3 months for evaluation. Wounds and scars will be evaluated at both 7-10 and 14 days and 3-4 months by both the researchers and the parents or care givers. A satisfaction survey will be administered to the parent or guardian. At 3-4 months, digital photographs of the healing lacerations will be graded for appearance by clinicians blinded to the repair method. The initial visit will be billed to their insurance and the follow-up visits will be free (non-registered).

Page numbers from a sponsor's protocol/grant may be referenced in 2b and 2c.

b) List your research objectives (specific aims & hypotheses of the study).

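### Equivalence is claimed, but the VAS is tested only for a difference and the 15 mm margin is set against the average difference, so a small or noisy trial can pass as equivalent

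*Combined protocol and SAP*

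**What the plan says.** Section 3d (data analysis) contains the whole statistical plan. For continuous outcomes, including the VAS, it says: "Differences between groups will be analyzed using the Student's t-test for independent samples". For binary outcomes: "Proportions will be compared using chi-square and the z-test for independent proportions". The error rate is "A significance level of 0.05 will be used in all analysis", with no sidedness given. The margin sentence reads: "Since this is an equivalence trial, a non-inferiority average difference of 15mm with the cosmesis VAS scale will be considered clinically equivalent". It is supported by the statement that "the minimal clinically important differences between two groups ranged from 10 to 15mm". The sample size of 18 per group is set for 90% power to detect a 15 mm difference.

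Section 2a (lay summary) states: "Our hypothesis is that there is no statistical difference in cosmetic outcomes between suture repair and non-repair of these injuries". Section 2b (objectives) states: "Our primary hypothesis is that there is no difference in cosmetic outcomes between suture repair and conservative treatment".

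The documents contain no confidence interval, no two one-sided tests (TOST), no null hypothesis placed at the margin, no direction for the margin and no SD for the VAS.

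**The concern.** The t-test takes zero difference as its null hypothesis. The plan states that same null as the hypothesis it hopes to support, so a non-significant result becomes the natural sign of success. But non-significance only means that zero was not ruled out. It does not rule out a 15 mm deficit, and it becomes easier to obtain as fewer patients return.

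The margin does not repair this, because it is set against the average difference with no requirement on precision. An estimate of 14 mm with a very wide interval would meet it. The sentence also joins equivalence (two-sided) with non-inferiority (one-sided), which need different rules, so two analysts could draw opposite conclusions from the same data.

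This is the trial's main conclusion. It would be used to argue that children with these wounds can go without suture repair, which section 3f gives as the accepted standard of care.

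**Working it through.** **Inputs.** From section 3d: margin 15 mm, 18 per group, power 90%, alpha 0.05, 50 to be enrolled, 40% attrition. From the Continuing Review form: 26 accrued (item 7) and 9 withdrawn for want of the 4-month visit (item 10). Assumptions: two-sided test, normal data, equal SDs, a 9/8 split of the remaining patients, and SD 20 mm as an alternative value.

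**Step 1. Reproduce the plan's 18 per group.** No SD is given, so the figure can only be solved backwards. By the normal formula n = 2·[SD·(1.960 + 1.282)/15]², n = 18 gives SD = 15·√(18/2)/3.242 = 13.9 mm. The exact noncentral-t solution is 13.5 mm. If alpha were one-sided, the normal formula would give 15.4 mm. The 18 is therefore attainable as a difference-test calculation, but it cannot be confirmed. I use 13.5 mm below.

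**Step 2. Evaluable numbers.** Planned: 18 + 18. From the plan's own enrolment and attrition: 50 × (1 - 0.40) = 30, or 15 per arm. From the Continuing Review form: 26 - 9 = 17, taken as 9/8.

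**Step 3. Chance of a non-significant t-test when conservative care is truly 15 mm worse.** The standard error is SE = SD·√(1/n₁ + 1/n₂) and the noncentrality is δ = 15/SE. The chance is P(|T| < t₀.₉₇₅), with T noncentral t on n₁ + n₂ - 2 df. For 18/18 and SD 13.5: SE = 13.5·√(2/18) = 4.50, δ = 3.33, critical value 2.03, result 10%. This is simply 1 minus the planned power.

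| Evaluable | SD 13.5 (implied) | SD 20 (assumed) |
|---|---|---|
| 18/18 | 10% | 41% |
| 15/15 | 16% | 49% |
| 9/8 | 43% | 70% |

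**Step 4. Average-difference rule.** If the true deficit is 15 mm, the estimate is centred on the boundary, so P(|estimate| < 15) is about 50% at any sample size and SD. At a true deficit of 20 mm the rule still passes 23% of trials at 18/18 and 30% at 9/8 (SD 20).

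**Step 5. Confidence-interval rules at the same true deficit of 15 mm (simulation).** The rule that the lower limit of the two-sided 95% CI exceeds -15 mm errs 2.5% of the time. The rule that the 90% CI lies within ±15 mm errs at most 5%. Both hold in every row of the table.

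**Step 6. Power of the confidence-interval rules when the true difference is zero (simulation).**

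| Evaluable | SD | Non-inferiority, 95% CI | Equivalence, 90% CI |
|---|---|---|---|
| 18/18 | 13.5 | 90% | 90% |
| 15/15 | 13.5 | 84% | 82% |
| 9/8 | 13.5 | 57% | 41% |
| 18/18 | 20 | 59% | 42–43% |

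At 9/8 and SD 13.5 the 95% CI half-width is about 2.131 × 6.56 = 14.0 mm, nearly the whole margin. Yet with no true difference the t-test is non-significant 95% of the time by construction.

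**The case against.** The strongest reply is that the plan never says a non-significant t-test will be taken as equivalence. Sections 2a and 2b state hypotheses, not decision rules, and the 15 mm could have been meant as the limit for an interval. On that view the rule is unspecified rather than wrong. It is fair to say the result can be read as equivalence rather than certainly will be. But no interval is specified anywhere, the margin is tied in words to the average, and a hypothesis of no statistical difference paired with a t-test makes non-significance the plan's own route to success.

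Several narrower points stand without changing the conclusion:

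- The t-test is the only test for the VAS, not for every outcome; the tests for proportions are also difference tests.
- The 50% applies if the average is used alone. If both conditions had to be met, the error at 18/18 and SD 13.5 would be 10%.
- Small numbers drive the non-significance reading; at a true 15 mm deficit they do not alter the 50%.
- The SDs are implied or assumed, the 9/8 split is assumed, and the IRB comments mention 18 subjects with follow-up rather than 17.
- Changing the rule does not rescue power if fewer than 18 per arm are evaluable or the SD is larger.

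On timing, the response to the IRB comments says enrolment will not continue, and the Continuing Review form proposes crowd-sourced Likert ratings, to which a 15 mm VAS margin would not carry over directly. The Event History shows that form was withdrawn, so section 3d remains the analysis text.

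**Conclusion.** The concern holds. The plan claims equivalence through a test of difference and a margin set against the point estimate, and neither limits the chance of a false claim. At a true 15 mm deficit that chance is 10% to 43% for the non-significance reading at the implied SD of 13.5 mm, and 41% to 70% at an assumed 20 mm, across 18/18, 15/15 and 9/8 evaluable patients. It is about 50% for the average-difference reading. A confidence-interval rule would hold it at 2.5% or 5%. The percentages rest on a two-sided 0.05 test for the implied SD, normal data and the assumed 9/8 split. The defect itself rests only on the wording of sections 2a, 2b and 3d. Because it decides the primary conclusion, it must be fixed before any analysis or report.

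**What to change.** In section 3d, replace the t-test decision for the VAS with one stated rule:

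- Estimate the mean VAS difference, conservative minus suture, with its confidence interval.
- If non-inferiority is meant, claim it only when the lower limit of the two-sided 95% CI is above -15 mm.
- If equivalence is meant, claim it only when the 90% CI (two one-sided tests at 5% each) lies wholly within -15 to +15 mm.
- Name one of the two as primary, and state alpha, sidedness and the assumed SD.
- State that a non-significant t-test does not support equivalence.
- Bring the hypotheses in sections 2a and 2b into the same terms.

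The cost is wording. With 18 evaluable per arm and SD 13.5 mm, power is about 90% under either rule, so the planned evaluable number need not change. With 15 per arm it is about 84% (non-inferiority) or 82% (equivalence). With 17 patients or a larger SD it falls well below that, and the trial would then be reported as inconclusive, which is the correct reading.

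### The 15 mm equivalence margin is the top of the 10–15 mm range of important differences that section 3(d) cites, so a deficit important by some of its sources can be labelled clinically equivalent

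*Combined protocol and SAP*

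**What the plan says.** All the relevant text is in section 3(d), apart from the scale, which is described in section 3(b).

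- Margin: "a non-inferiority average difference of 15mm with the cosmesis VAS scale will be considered clinically equivalent".
- Source of the margin, in the next sentence: "Previous studies have determined that the minimal clinically important differences between two groups ranged from 10 to 15mm (4,15,16").
- Test and level: "Differences between groups will be analyzed using the Student's t-test for independent samples" and "A significance level of 0.05 will be used in all analysis". Sidedness is not stated, and no confidence interval or two one-sided tests rule is given.
- Sample size: "A sample size of 18 patients per group will be needed to provide a power of 90% with 0.05 alpha error". The calculation uses the same 15 mm as its target effect, and no SD is given.
- Scale: "The frequently used scale is a 100mm continuous line", running from worst to best scar.

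Section 2(b) gives the primary hypothesis as no difference in cosmetic outcome, and the aim as showing savings in time, money and pain without loss of cosmetic satisfaction. No reason is given for taking the upper end of the cited range as the margin.

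**The concern.** The margin equals the maximum of the range of important differences that the plan cites. Mean deficits from 10 mm up to just under 15 mm are therefore in two places at once: inside the zone the plan labels clinically equivalent, and at or above the importance threshold of at least some of the studies it relies on.

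The label is also unconditional. It attaches to an average difference, and the plan does not say whether that means the observed mean difference or a confidence limit. A reader of the final report could not tell whether a 10 to 15 mm worse scar had been excluded.

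The wording matters because section 3(f) names suture repair as the accepted standard of care, and section 8(d) says a favourable result would let children avoid it.

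**Working it through.** **1. The overlap.** Margin: 15 mm. Cited range: 10 to 15 mm. The overlap is 10 mm up to 15 mm. This step needs no SD.

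**2. Reproducing 18 per group.** The documents give no SD, so 18 cannot be verified independently. It can only be inverted to see which SD it implies, using n = 2 × [SD × (z_α + z_β) / 15]², rounded up:

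- Two-sided 0.05, 90% power, SD 13.5: 2 × [13.5 × (1.960 + 1.282) / 15]² = 17.0 (17.02 unrounded), giving 18.
- One-sided 0.05, 90% power, SD 15: 2 × [15 × (1.645 + 1.282) / 15]² = 17.1, giving 18.
- Two one-sided tests with no true difference (z_β = 1.645): an SD of about 13.3–13.7 mm at 0.05 each, or 12.1–12.5 mm at 0.025 each.

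The implied SD is therefore roughly 12 to 15 mm, depending on the rule intended. That range is an assumption from here on.

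**3. Chance that a truly worse scar meets the 15 mm margin, 18 per group.** SE = SD × √(2/18) = SD/3, with 34 degrees of freedom. For a true deficit δ:

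- Confidence-limit rule: P(T > t_crit), where T is noncentral t with noncentrality (15 − δ)/SE. t_crit is 1.691 for a one-sided 95% limit and 2.032 for a 97.5% limit.
- Point-estimate rule: Φ[(15 − δ)/SE].

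| SD (mm) | SE (mm) | δ = 10, 95% limit | δ = 10, 97.5% limit | δ = 10, point estimate | δ = 12, 95% limit | δ = 12, point estimate |
|---|---|---|---|---|---|---|
| 12 | 4.0 | 34% | 23% | 89% | 18% | 77% |
| 13.5 | 4.5 | 29% | 19% | 87% | 16% | 75% |
| 15 | 5.0 | 25% | 16% | 84% | 15% | 73% |

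Example: SD 13.5, δ = 10. Noncentrality = 5/4.5 = 1.11, giving 0.289 with the 95% limit and Φ(1.11) = 0.867 with the point estimate.

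**4. Which observed deficits pass.** At SD 13.5 the 90% two-sided half-width is 1.691 × 4.5 = 7.6 mm. Under an interval rule only observed deficits below 15 − 7.6 = 7.4 mm meet the margin. Under the point-estimate reading any observed deficit below 15 mm does.

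**5. How often a ±10 mm conclusion would be reached with no true difference.** This is the probability that the whole 90% interval lies within ±10 mm (exact two one-sided tests power):

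- 18 per group: 58% at SD 12, 41% at SD 13.5, 25% at SD 15.
- 15 per group (50 enrolled less 40% attrition = 30), SD 13.5: 27%.
- About 9 per group (26 accrued less 9 withdrawn = 17, in the Continuing Review form; an even split is assumed), SD 13.5: about 5%.

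For comparison, at 18 per group and SD 13.5 the interval lies within ±15 mm 90% of the time.

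**The case against.** **15 mm lies inside the cited range.** A reader might infer that the plan itself calls a 10 mm deficit important and then contradicts itself. The text does not support that. It reports a range across previous studies, so at least one source put the threshold near 15 mm. The documents do not show which source gave which value, or whether any concerned children's hands and feet. Choosing one end of a cited range is a disclosed judgement. This stands, and it is why the point concerns the label and not the legitimacy of 15 mm as a margin.

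**The margin should be 10 mm.** A reader might also infer this, but nothing in the documents requires it. It would multiply the sample by (15/10)² = 2.25, from 18 to 41 per group.

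**An interval rule is already strict.** With a 95% limit and SD 13.5, an observed deficit of 10 to 14 mm would fail. That is true, but section 3(d) states no interval rule. Even under one, a limit falling between 10 and 15 mm does not exclude a deficit of that size.

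**The SD is assumed.** The percentages do depend on it; at SD 20, the 29% becomes 18%. The overlap in step 1 does not.

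**The point may be overtaken.** In the Continuing Review form the study team proposes crowd-sourced Likert ratings, and in the Comments section it says enrolment has ended. The Event History shows that submission as withdrawn, so the VAS plan in 3(d) remains the text under review. If the VAS were replaced, the millimetre thresholds would not carry over.

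**Conclusion.** The concern holds in a limited form. Section 3(d) allows the label clinically equivalent to attach to a 10–15 mm worse scar that some of its own cited studies would count as important, and nothing elsewhere in the documents resolves this.

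The size depends mainly on the unstated decision rule. A true 10 mm deficit would meet the margin in roughly one trial in six to one in three under a confidence limit, but in more than four in five if the observed mean is compared with 15 mm. These figures rest on 18 evaluable per group, equal allocation, normally distributed VAS scores and an assumed SD of 12–15 mm.

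This is a worthwhile, inexpensive correction to what the trial may claim. It does not show that the margin is invalid.

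**What to change.** In section 3(d):

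1. Keep 15 mm as the powered margin.
2. State that it is judged by a named confidence interval for the mean VAS difference, not by the point estimate. One example is the 90% two-sided interval, which matches one-sided 0.05.
3. Replace the unconditional label with wording graded on that interval:
   - Within ±10 mm: *no clinically important difference*.
   - Within ±15 mm but not ±10 mm: *differences above 15 mm excluded; a difference of 10–15 mm, important by some cited studies, not excluded*.

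Symmetric limits fit the plan's description of itself as an equivalence trial, although the harm of interest is a worse scar without suturing.

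The cost is a few sentences and no added patients. The price is a weaker claim in many cases: the stronger wording will often be out of reach even if the two treatments are identical (step 5 of the working), and the plan should say so in advance. The thresholds apply only while the VAS remains the outcome measure.
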